**Recommended dose constraints for fractionated radiation < 3 Gy per fraction:**

Lung	V20Gy (Rt + Lt lung minus PTV)	< 37%
Mean (Rt + Lt lung minus GTV)	< 20 Gy	
Esophagus	Mean	< 34 Gy
Heart	V60 Gy	< 33%
	V45 Gy	< 66%
	V 40 Gy	< 100%
Brachial Plexus	Max dose	< 66 Gy
Spinal Cord	Max dose	< 48 Gy

A Randomized Trial of Consolidative Immunotherapy with vs without Thoracic Radiotherapy and / or Stereotactic Body Radiation Therapy (SBRT) after First-line Systemic Therapy for Metastatic NSCLC  
 Wake Forest Baptist Comprehensive Cancer Center  
 WFBCCC # 62718

## 8.0 Study Activities and Patient Assessment

### 8.1 Study Calendar

Study	Details	Enrollment 	Prior to Randomization	1 mo F/U 	Every 3 mo For 3 years	Every 6 mo For 2 years
History, Physical		All		PE PS	PE PS	PE PS
PFT's (Spirometry, Lung volume & DLCO)			X 			
RT-related Toxicities and Immunotherapy related toxicities	Graded per NCI CTCAE, v. 5.0	X 		X	X	X
MRI of Brain FDG PET/CT Base of skull to mid-thigh			X 			
CT of Chest Abdomen and Pelvis	To include lungs, liver, and adrenal glands	X 		X 	X 	X 
Serum or urine pregnancy test	Within 1 week prior to RT (if childbearing potential)	X				
Blood sample collection			X	X		
Response Assessment	Determined by a radiologist utilizing RECIST criteria	X		X	X	X
Appendix H		X				
Appendix C,D			X			
Appendix E				X		
Appendix F				X		
Appendix G, J, L				X	X	X

1. Enrollment and randomization must occur after completion of 4 cycles of standard of care systemic therapy, but no later than 180 days from the first day of cycle 1 of standard of care systemic therapy. Randomization will occur no later than 21 days from time of enrollment.
2. CT Chest Abdomen pelvis demonstrating no evidence of progression per RECIST v1.1, must be performed after completion of 4 cycles of standard of care systemic therapy prior to enrollment. Ideal if CT prior to enrollment has IV contrast but not required.
3. PFTs within at least **6 months** of enrollment
4. Baseline evaluation should document any residual toxicity from previous therapies.
5. PET and MRI brain must be completed prior to randomization.
  - a. If PET has been performed within 30 days of enrollment, scan does not need to be repeated.
  - b. If MRI brain has been performed within 90 days of enrollment, scan does not need to be repeated.
6. Followup CT Chest abdomen pelvis to be performed with IV contrast unless medically contraindicated by renal function or contrast allergy.
  - a. For patients randomized to the radiation arm – the first CT will be performed 1 month after the last treatment of radiation per standard of care
  - b. For patients randomized to the immunotherapy arm – the first CT will be performed 1 month after the completion of the 2nd cycle of immunotherapy per standard of care
  - c. The schedule above is standard of care for imaging followup. Should a patient be enrolled after starting maintenance immunotherapy and after their first 3 month followup scan, then they may be allowed to switch to 6 months interval imaging at 3yrs from the end of chemo-immunotherapy, rather than a full 3 yrs from the date of randomization in accordance with standard of care. At discretion of treating oncologist.
7. Definition of 1 mo. or 30 day followup
  - a. For patients randomized to RT, this time point is considered 30 days +/- 14 days from end of all radiation therapy treatments
  - b. For patients randomized to immunotherapy alone, this time point is considered 30 days +/- 14 days from the end of the 2nd cycle of on protocol maintenance immunotherapy
8. Two tubes of whole blood may be collected at time of registration or any time prior to initiating any protocol directed therapy and at the 1 month follow up +/- 2 weeks.
9. If patients progress and are not eligible for randomization, or if they progress at any point on the study, they are only followed w appendix L for survival after the point of progression

**FOLLOWUP VISITS AND CT SCANS HAVE A FLEXIBILITY WINDOW OF +/- 8 WEEKS AROUND THE TIME POINT LISTED ON THE STUDY CALENDAR**

## 8.2 Study Activities – Required Evaluations

- 8.2.1** A medical history, physical examination, weight, NCI comorbidities, and assessment of ECOG performance status within 12 weeks of enrollment. ECOG status will be documented at time of the radiation oncology consult in the electronic medical record.
- 8.2.2** A CT chest abdomen pelvis demonstrating no evidence of progression per RECIST v1.1 that has been performed after completion of 4 cycles of chemo-immunotherapy but no later than 180 days from the first day of chemo-immunotherapy.
- 8.2.3** A PET/CT and MRI brain will be performed, either prior to randomization or a PET that is within 30 days of enrollment, or MRI brain within 90 days of enrollment may be used for purposes of randomization.
- 8.2.4** Biopsy or cytology demonstrating a diagnosis of non-small cell lung carcinoma.
- 8.2.5** Two tubes of whole blood will be collected via routine blood draw and saved for future exploratory biomarker studies as listed on the study calendar, at time of registration and at the 1 month follow up +/- 2 weeks. For radiation patients this is 1 month after the last treatment of radiation. For immunotherapy only patients, this is 1 month after the second dose of maintenance immunotherapy on study.
- 8.2.6** Serum or urine pregnancy test within 1 week of RT in women of child bearing potential.

## 8.4 During Follow Up

- 8.4.1** The dates of follow up and protocol related assessments are defined as below. Follow up and protocol directed assessments must be performed +/- 8 weeks from each specified FU time point.

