### For patients randomized to radiation:

Patients will undergo CT imaging of chest/abdomen/pelvis at 1 month after the last treatment of radiation is completed. Subsequently, they will undergo CT imaging of chest/abdomen/pelvis every 3 months for 3 years, then every 6 months for 2 years per standard of care.

**For patients randomized to continue maintenance immunotherapy:** alone, they will undergo CT imaging of chest/abdomen/pelvis at 1 month after the 2nd cycle of protocol directed maintenance immunotherapy has been delivered. Subsequently, they will undergo CT imaging of chest/abdomen/pelvis every 3 months for 3 years, then every 6 months for 2 years per standard of care.

Should a patient be enrolled after starting maintenance immunotherapy and after their first 3 month followup scan, then they may be allowed to

switch to 6 months interval imaging at 3yrs from the end of chemo-immunotherapy, rather than a full 3 yrs from the date of randomization in accordance with standard of care. At discretion of treating oncologist.

If a patient, has suspicion of progression but requires closer interval followup than 3 months or additional imaging, this is allowable at the discretion of the treating physician. If ultimately, they are deemed to not have progressive disease, they would then resume the schedule listed in the study calendar above.

**8.4.2** Patients who progress on or after protocol directed therapy will be followed for survival only as per Appendix L without further protocol follow up requirements. This includes progression of the protocol treated tumors, non-protocol treated tumors and the development of new metastatic disease. Tumor progression will be determined by RECIST criteria.

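### The ±8-week window on the three-monthly CTs lets effective scan spacing double without a recorded deviation, and a systematic arm difference in spacing could bias PFS

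*Combined protocol and SAP*

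**What the plan says.** After a first CT, both arms are imaged "every 3 months for 3 years, then every 6 months for 2 years per standard of care" (8.4). Section 8.4.1 sets the tolerance: "Follow up and protocol directed assessments must be performed +/- 8 weeks from each specified FU time point". The capitalised note after the study calendar footnotes confirms that imaging is included: "FOLLOWUP VISITS AND CT SCANS HAVE A FLEXIBILITY WINDOW OF +/- 8 WEEKS AROUND THE TIME POINT LISTED ON THE STUDY CALENDAR".

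The first follow-up CT is tied to different events in the two arms. In the radiation arm it comes 1 month after the last radiation treatment. In the immunotherapy-alone arm it comes "at 1 month after the 2 nd cycle of protocol directed maintenance immunotherapy has been delivered". For the 1-month visit, footnote 7 of the calendar and Appendix F give a much tighter window; in the radiation arm "this time point is considered 30 days +/- 14 days from end of all radiation therapy treatments".

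Response is "Determined by a radiologist utilizing RECIST criteria" (8.1). Closer or additional imaging on suspicion of progression is permitted: "this is allowable at the discretion of the treating physician" (8.4). PFS runs from the start of first-line systemic therapy (5.1 and 8.10), and the arms are compared by log-rank test (14.1). Sections 8.10 and 14.1 contain no rule for late or missed scans, no interval-censored analysis and no sensitivity analysis for scan timing. No blinded or central read is stated. Section 9.6.4.2 provides only periodic review of progression scoring between the overall and affiliate principal investigators.

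**The concern.** Progression found by imaging is dated at the scan that shows it, so recorded PFS depends on when scans happen as well as on the disease. If one arm is scanned less often, its progressions are dated later and it looks better with no treatment effect. Trials normally control this by holding both arms to the same schedule within a window clearly shorter than the interval. Here the full window is wider than the interval, so the three-monthly schedule can be thinned to roughly six-monthly without anyone recording a departure. There is no sham procedure, so treating teams who know the arm schedule the scans. The primary result could then carry a scan-timing component that the analysis plan has no means of detecting.

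**Working it through.** **1. Window arithmetic (8.4, 8.4.1)**

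The interval is 3 months, or 13 weeks. The window is ±8 weeks, a full width of 2 × 8 = 16 weeks. Weeks below are counted from the origin of the three-monthly series; the result does not depend on what that origin is.

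- Month 3: 13 ± 8 = weeks 5–21.
- Month 6: 26 ± 8 = weeks 18–34.
- Overlap: 16 − 13 = 3 weeks (weeks 18–21). A single CT there lies inside both windows.
- Longest gap between consecutive compliant CTs: 34 − 5 = 13 + 16 = 29 weeks = 203 days, about 6.7 months.
- Sustainable pattern: one CT in weeks 18–21 (months 3 and 6), the next in weeks 44–47 (the overlap of months 9 and 12), and so on, 26 weeks apart. The documents do not say whether one CT may count for two time points. If it may not, two CTs placed close together inside each overlap give nearly the same effective spacing.
- Six-monthly phase: 26 > 16, so windows do not overlap. The longest gap is 26 + 16 = 42 weeks.
- 1-month visit: 30 − 56 = −26 days, so ±8 weeks would open the radiation-arm window 26 days before radiation ends. This conflicts with the stated ±14 days.

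**2. Design figures used as a yardstick (13.1)**

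The plan randomizes 112 patients 2:1 (about 75 and 37), with medians of 8 and 15 months, so HR = 8/15 = 0.53. By Schoenfeld's formula the events needed are (1.96 + 0.84)² / [(2/3)(1/3)(ln 0.533)²] = 7.85 / 0.0878, or 90. With 54 months of accrual and 60 months in total, about 86.5 events are expected. Power is then Φ(√(86.5 × 2/9) × 0.629 − 1.96) = Φ(0.80) = 0.79, which agrees with the stated 0.80.

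**3. Effect of scan timing when there is no treatment effect**

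Taken from the documents: 75 versus 37 patients, PFS timed from first-line start, two-sided log-rank test at 5%. Assumed, because the documents do not give them: exponential progression times; a post-randomization median of 100 or 180 days with 10% of events dated exactly, or of 4 or 8 months with 15%; and randomization staggered over roughly 12–26 weeks after first dose (day 180 is the protocol's limit). Ranges span these settings. In the one-arm and 26-versus-13-week rows, the radiation arm is the later or sparser one.

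| Scan timing | Apparent HR | Two-sided false positives |
|---|---|---|
| Both arms on time | about 1.00 | 5–6% |
| Both arms random within ±8 weeks | 0.99–1.00 | 5–6% |
| One arm steadily 4 weeks late | 0.94–0.98 | 5–6% |
| One arm 4 weeks late, other 4 weeks early | 0.96–0.99 | about 6% |
| One arm steadily 8 weeks late | 0.90–0.95 | 6–10% |
| One arm 8 weeks late, other 8 weeks early | 0.90–0.95 | 7–9% |
| One arm about every 26 weeks, other every 13 | 0.77–0.90 | 9–22% |
| Same, with 40% of events dated exactly between scans | 0.86–0.93 | 8–13% |

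With 1,500 replicates the Monte Carlo standard error at 5% is √(0.05 × 0.95 / 1500) = 0.6 percentage points, so differences of about one point are noise.

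A steady shift does little because every scan moves together and the spacing stays at 13 weeks. The effect becomes material only when the spacing itself differs between arms.

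**The case against.** The strongest reply is that both arms have the same nominal three-monthly schedule, described as standard of care, and that windows are tied to calendar time points, so lateness does not accumulate. Scans outside the window can be logged on the deviation form in Appendix P, a radiologist applies RECIST, and extra imaging is allowed when progression is suspected. Undirected variation costs only precision. Nothing in the documents suggests that one arm would be scanned half as often as the other, and even that pattern does not approach the design hazard ratio of 0.53.

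All of this stands as to likelihood and size. It does not remove the defect. Appendix P can flag only what falls outside the window, and 26-week effective spacing falls inside it. Extra scans on suspicion reduce the bias (last row of the table) but do not abolish it. A radiologist's read does not correct the date on which a scan was taken.

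A reader might go further and infer that routine scheduling differences, or a lag of a few weeks in one arm, would by themselves create a PFS difference. The documents do not support that. A simulation that scans every patient on identical days counted from randomization can seem to show it, but it is measuring the ordering of tied event dates: in such a model a lag of one day looks more harmful than a lag of four weeks. Under 8.10 the PFS clock starts at first-line therapy and randomization follows at varying times, which breaks up that common grid. The 4-week effect then nearly vanishes.

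**Conclusion.** The concern holds in limited form. It is certain from the text that the CT window exceeds the interval, that adjacent windows overlap by 3 weeks, that compliant gaps reach 29 weeks, and that roughly 26-week effective spacing leaves no deviation. It is also clear that the plan states no safeguard against a scan-timing difference between arms.

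The bias is conditional. Random timing and steady lags of up to 4 weeks are negligible, and a steady 8-week lag has a small effect. A systematic difference of about 26 versus 13 weeks could raise the two-sided error from 5% to 9–22%, with a spurious hazard ratio of about 0.77–0.90 if the radiation arm is the sparser one. If the control arm were sparser, the bias would run the other way. These sizes rest on the assumed post-randomization median of about 3–8 months and on 10–15% of events being dated exactly. With 40% dated between scans they fall to 0.86–0.93 and 8–13%. The documents permit such a difference but give no evidence that it will arise. The change is worth making because it is cheap and the plan could not otherwise detect the problem.

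**What to change.** For CT and response assessments in the three-monthly phase, replace ±8 weeks in 8.1 and 8.4.1 with a window below half the interval (6.5 weeks) so that windows cannot overlap. With ±2 weeks the longest compliant gap becomes 13 + 4 = 17 weeks; with ±4 weeks it becomes 13 + 8 = 21 weeks. The wide window can stay for clinic-only visits.

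Reconcile the general window with the ±14 days already stated for the 1-month visit in footnote 7 and Appendix F.

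In 14.1, add a report of actual scan dates and intervals by arm, and one prespecified sensitivity analysis, such as interval-censored PFS or PFS with progression dated to the scheduled visit.

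The cost is a short amendment and a small addition to the analysis. No scans are added. More late scans will be logged as deviations, and sites lose some scheduling freedom. For patients already scanned under the current window, the timing report and sensitivity analysis are the only remedy.

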### For patients randomized to radiation:

Patients will undergo CT imaging of chest/abdomen/pelvis at 1 month after the last treatment of radiation is completed. Subsequently, they will undergo CT imaging of chest/abdomen/pelvis every 3 months for 3 years, then every 6 months for 2 years per standard of care.

**For patients randomized to continue maintenance immunotherapy:** alone, they will undergo CT imaging of chest/abdomen/pelvis at 1 month after the 2nd cycle of protocol directed maintenance immunotherapy has been delivered. Subsequently, they will undergo CT imaging of chest/abdomen/pelvis every 3 months for 3 years, then every 6 months for 2 years per standard of care.

Should a patient be enrolled after starting maintenance immunotherapy and after their first 3 month followup scan, then they may be allowed to

switch to 6 months interval imaging at 3yrs from the end of chemo-immunotherapy, rather than a full 3 yrs from the date of randomization in accordance with standard of care. At discretion of treating oncologist.

If a patient, has suspicion of progression but requires closer interval followup than 3 months or additional imaging, this is allowable at the discretion of the treating physician. If ultimately, they are deemed to not have progressive disease, they would then resume the schedule listed in the study calendar above.

**8.4.2** Patients who progress on or after protocol directed therapy will be followed for survival only as per Appendix L without further protocol follow up requirements. This includes progression of the protocol treated tumors, non-protocol treated tumors and the development of new metastatic disease. Tumor progression will be determined by RECIST criteria.

#### **8.5 Duration of Therapy**

In the absence of treatment delays due to adverse events, treatment may continue for until one of the following criteria applies:

- Disease progression
- Intercurrent illness that prevents further administration of treatment,
- Unacceptable adverse event(s),
- Patient decides to withdraw from the study, or
- General or specific changes in the patient's condition render the patient Unacceptable for further treatment in the judgment of the investigator.

If a patient is unable to complete a total of 2 years of maintenance Immunotherapy due to toxicity, declining therapy, or intercurrent illness, or any other reason, they will continued to be followed on study until a progression event, death, or withdrawal from study.

#### **8.6 Duration of Follow Up**

All patients should be followed for study endpoints for a minimum of six months. Afterwards patients without progression will be followed as listed in the study calendar.

#### **8.7 Response determination:**

The use of international criteria proposed by the Response Evaluation Criteria in Solid Tumors (RECIST) Committee is required for response assessment. During follow up, PET imaging can be used to assist in adjudicating decisions regarding local failure as the SBRT process can in itself result in increases in the imaging abnormality on either a temporary or permanent but stable basis due to radiotherapy treatment effects such as tissue fibrosis.

#### **8.8 Regional failure:**

New nodal disease  $\geq$  1cm in size within the lung, hilum, or mediastinum. Equivocal nodes should be assessed with FDG PET or biopsy

#### **8.9 Distant disease:**

Appearance of distant cancer deposits consistent with metastatic spread. PET-CT or biopsy encouraged but not required.

#### **8.10 Survival Definitions**

A Randomized Trial of Consolidative Immunotherapy with vs without Thoracic Radiotherapy and / or Stereotactic Body Radiation Therapy (SBRT) after First-line Systemic Therapy for Metastatic NSCLC  
 Wake Forest Baptist Comprehensive Cancer Center  
 WFBCCC # 62718

**Progression-Free Survival**

Progression-Free Survival is defined as the duration from the start of first line standard of care systemic therapy to the time of progression, death, or date of last contact; those lost to follow-up will be censored.

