**3.0 Patient Selection**

**ENROLLMENT**

- Patients are eligible for enrollment if they have metastatic NSCLC and have undergone at least 4 cycles of upfront standard of care systemic therapy (usually this will consist of combination chemo immunotherapy, but in some cases may be chemotherapy or immunotherapy alone). Patients must have a CT chest abdomen pelvis (ideally with IV contrast) performed after the point of completion of 4 cycles of systemic therapy, but no later than 180 days from the first day of systemic therapy. This CT scan must be completed within 180 days of the first day of systemic therapy, and must demonstrate no evidence of disease progression per RECIST v1.1.
- Patients may start their standard of care maintenance immunotherapy at the discretion of their treating medical oncologist prior to enrollment. Patients must be enrolled AND randomized no later than 180 days from the first day of cycle 1 of systemic therapy. The first day of cycle 1 of combined systemic therapy is considered day # 1. At most, an additional 179 days may elapse from this point to remain eligible for inclusion on this study.

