## 5.0 Outcomes

### 5.1 Primary Outcome

- 5.1.1 Progression-free survival from the date of starting first line standard of care systemic therapy.

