### 5.2 Secondary Outcome

- 5.2.1 Overall survival over 5 years from the date of starting first line standard of care systemic therapy.
- 5.2.2 In patients who experience subsequent failures after initiating protocol directed therapy, we will assess whether these failures occurred at known or new sites of disease.
- 5.2.3 Frequency of adverse events per CTCAE v5.0

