**Overall Survival**

Overall Survival is defined as the duration from the start of first line standard of care systemic therapy to the date of death or date of last contact; those lost to follow-up will be censored.

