**14.0 Data Analysis**

**14.1 Analysis of Primary Objective**

Actuarial progression-free survival will be determined using the product-limit method of Kaplan and Meier. We will compare unadjusted median PFS between the 2 arms using a log-rank test. We will also use a proportional hazards model to compare progression-free survival between the two groups, adjusting for key covariates such as age, performance (ECOG) status, response to initial systemic therapy vs stable disease, the presence or absence of brain metastases, PD-L1 expression (< 1% vs > 50%), tumor histology (adenocarcinoma vs non-adenocarcinoma), number of disease sites treated (1-3 sites vs 4-6 sites vs 7-8 sites) and length of time between date of first chemotherapy-immunotherapy treatment and randomization date..

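### PFS and OS are timed from the first systemic dose rather than randomization, so medians and curves carry about 3 to 6 months of near-guaranteed event-free time and the Cox lead-in covariate is part of its own outcome

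*Combined protocol and SAP*

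**What the plan says.** The origin is stated consistently. Section 5.1.1 gives the primary outcome as "Progression-free survival from the date of starting first line standard of care systemic therapy". Section 5.2.1 gives "Overall survival over 5 years from the date of starting first line standard of care systemic therapy". Section 8.10 repeats the same start for PFS ("duration from the start of first line standard of care systemic therapy to the time of progression") and for OS ("duration from the start of first line standard of care systemic therapy to the date of death"). Section 13.1 quotes its planning medians, 8 and 15 months, from the first chemo-immunotherapy treatment.

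Randomization comes much later. Under section 3.0, patients must "have undergone at least 4 cycles of upfront standard of care systemic therapy" and have a CT after those cycles without progression. Section 3.3 then requires restaging without progression, and patients who progress at restaging are not randomized. The outer limit is also in section 3.0: "Patients must be enrolled AND randomized no later than 180 days from the first day of cycle 1 of systemic therapy".

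Section 14.1 applies Kaplan-Meier, the log-rank test and a Cox model. Its covariates include the "length of time between date of first chemotherapy-immunotherapy treatment and randomization date". Section 14.2 carries these methods to OS. Neither section specifies delayed entry or an analysis timed from randomization.

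**The concern.** Objective 2.1.1 compares patients randomized to two strategies, so the question concerns what happens after randomization. On the first-dose clock each randomized patient's time is a lead-in, survived by selection, plus the time after randomization. Two things follow.

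First, the curves and medians describe the selection window together with the treatment period. Patients are counted as at risk during months in which they could not have failed and still be in the trial.

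Second, the lead-in interval is both a predictor and a piece of the response. A longer lead-in lengthens the outcome by construction, so its coefficient is pushed toward looking protective even when the timing of randomization has no bearing on prognosis.

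At stake are the medians that readers will quote and a covariate coefficient that cannot be interpreted as it stands.

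**Working it through.** **1. The plan's own figure (section 13.1).** Inputs: 112 patients at 2:1, medians 8 and 15 months, two-sided alpha 0.05, power 0.80, 54-month accrual, 60 months in total.

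- Hazard ratio: 8/15 = 0.533.
- Events needed: (1.96 + 0.84)² / [(2/3)(1/3)(ln 0.533)²] = 7.85 / (0.222 × 0.395), about 90.
- Expected events with exponential PFS: event probabilities 0.874 (control) and 0.721 (experimental), so 112 × (0.874/3 + 2 × 0.721/3) = 86.5.
- Power: Φ(0.629 × √(86.5 × 0.222) − 1.96) = 0.787.

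The stated 0.80 is reproduced closely. The calculation lets events occur from time zero. Under an 8-month exponential starting at the first dose, 1 − 0.5^(2.8/8) = 21% to 1 − 0.5^(5.9/8) = 40% of patients would have failed before randomization; such patients are not in this trial.

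**2. Length of the lead-in, L.** The upper limit is fixed: 180/30.4 = 5.9 months. The lower limit is an assumption, because section 6.1 gives a 3-week cycle only for pembrolizumab consolidation. Four 3-week cycles are 84 days, or 2.8 months; counted to day 1 of cycle 4, 63 days, or 2.1 months. A uniform spread over 2.8 to 5.9 has mean 4.35.

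**3. Medians.** With T = L + R, where R is time after randomization, a fixed L gives median(T) = L + median(R).

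| L (months) | 8 / 15 after randomization is reported as | 8 / 15 from first dose means, after randomization |
|---|---|---|
| 2.8 | 10.8 / 17.8 | 5.2 / 12.2 |
| 4.5 | 12.5 / 19.5 | 3.5 / 10.5 |
| 5.9 | 13.9 / 20.9 | 2.1 / 9.1 |

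The lead-in is 2.8/8 = 35% to 5.9/8 = 74% of the planned control median. The height of the curve moves too: for an 8-month control median after randomization, PFS at 12 months is 0.5^(12/8) = 35% from randomization, but 0.5^((12 − L)/8) = 45%, 52% and 59% from first dose for the three values of L.

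**4. The lead-in covariate.** Simulated trials: 75 and 37 patients, L uniform on 2.8 to 5.9, exponential PFS after randomization, 54-month accrual, analysis at month 60, true lead-in effect zero.

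| Medians after randomization, control / experimental | Lead-in HR per month, first-dose clock | Nominally significant |
|---|---|---|
| 8 / 15 | 0.927 (second run 0.922) | 10.5% (11.7%) |
| 8 / 8 | 0.903 | 12% |
| 3.65 / 6.9 | 0.867 | 25% |
| 3.65 / 3.65 | 0.822 | 43% |

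On the randomization clock the HR is 1.00 throughout, nominally significant in 3% to 6% of trials. The 3.65-month row is roughly what an 8-month median from first dose leaves after the mean lead-in: 8 − 4.35 = 3.65.

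**5. The treatment comparison.** In the 3.65 / 6.9 scenario the treatment HR is 0.524 from randomization and 0.527 from first dose, with power 85.1% and 84.7%; under the null, rejection is 4.9% and 5.5%. In the 8 / 15 scenario log-rank power is 0.792 and 0.795, the Cox HR is 0.522 on both clocks, and with equal medians of 8 the type I error is 0.051 on both.

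**6. Five-year OS.** The documents give no planning OS for these arms. Assume exponential OS after randomization with medians of 12, 18 and 24 months. From randomization, 0.5^(60/m) = 3.1%, 9.9% and 17.7%. From first dose at the mean lead-in, 0.5^(55.65/m) = 4.0%, 11.7% and 20.0%. The shift is about 1 to 2 points.

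**The case against.** The strongest reply is that the primary objective is a between-arm comparison and that comparison is sound. Randomization gives both arms the same lead-in distribution, and step 5 shows no material change. This stands in full. A reader might infer a classic immortal-time bias favoring radiation; the documents do not support that, because the event-free period precedes randomization and applies equally to both arms.

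The origin is also deliberate, disclosed and the same in sections 5, 8.10 and 13.1, so it is not an internal contradiction, and a median labeled as counted from first dose is not false. This too stands. But labeling does not make the figure comparable with first-dose results in patients who could fail from day 1.

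Other strong readings should be resisted:

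- Six- and 12-month PFS rates are not planned outputs. They can only be read off the planned curves. The one named horizon is 5 years for OS, and it hardly moves.
- The 43% rate needs both a short post-randomization median and no treatment effect. With medians of 8 and 15 it is about 10% to 12%. Section 14.1 includes the covariate for adjustment and plans no inference on its coefficient.
- The stage III durvalumab trial in section 1.6 is timed from randomization, but it is a different population and a weak comparator here.
- For PFS the guarantee runs to the qualifying scans, which may precede randomization by some weeks; hence near-guaranteed. Survival to randomization is certain.

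Finally, simply moving every clock to randomization would fail. Objective 2.2.1 estimates OS in all patients and section 14.2 examines enrolled patients who were not randomized; they have no randomization date.

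**Conclusion.** The point holds as one about estimates, not about the validity of the test. In both randomized arms the Kaplan-Meier medians rise by about the lead-in: 2.8 to 5.9 months if first-line cycles last 3 weeks, with only the upper end fixed by the protocol. The lead-in coefficient is biased toward protection by construction, by about 0.82 to 0.93 per month, with false significance in about 10% to 40% of simulated trials. Those sizes rest on an assumed uniform lead-in and exponential PFS after randomization; the direction does not.

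The log-rank test, treatment hazard ratio, power and type I error are essentially unchanged, and 5-year OS shifts by about 1 to 2 points under assumed medians of 12 to 24 months. A change is advisable because the medians are core outputs and the remedy is cheap. The trial's main conclusion is not threatened.

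**What to change.** - In sections 5.1.1, 5.2.1, 8.10, 14.1 and 14.2, time PFS and OS from the date of randomization for every randomized comparison. Keep the lead-in interval as a covariate; on that clock it is an ordinary baseline variable.
- In section 13.1, restate the planning medians on the same clock. As step 3 shows, 8 and 15 months mean different things on the two clocks.
- For OS in all enrolled patients and in those enrolled but not randomized (2.2.1, 14.2), use the enrollment date as origin, or the first-dose clock with delayed entry at enrollment.
- Make any first-dose curves for randomized patients supplementary, with delayed entry at randomization, and label them as conditional on reaching randomization. Delayed entry does not remove all the guaranteed time: the curve stays at 100% until the first entry. With first entry at 2.8 months and a 3.65-month control median after randomization, it gives 2.8 + 3.65, about 6.5 months, against about 8.1 without delayed entry.

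The cost is an amendment to the primary endpoint's definition and to the planning text. No new patients, visits or data are needed, since section 14.1 already uses the randomization date. The visible downside is that reported medians become shorter by about the lead-in in both arms.
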